**Table 3: Re-Treatment Evaluation on Study** 

Phase	Study Visits									
Cycle			1			2		3	"X"	
$\mathrm{Day}^1$	Day 1	Day 8	Day 15	Day 22	Day 1	Day 15	Day 1	Day 28+/-4	Day 1	As clinically indicated
History and Physical Exam	X				X		X		X	
Head and Neck Exam 	X				X					
ECG	X		X8		X		X		$X^{10}$	
Dermatology Exam 							X			X
CBC w/ diff, Platelets	X	X8	X8	X8	X	X8	X	X	X	
Smear Review	X	X8	X8	X8	X		X		X	
COMP, LDH	X				X		X	X	X	
Phosphorus, Uric Acid	X	X8	X8	X8						
PT/PTT										
HIV, Hepatitis B and C Testing										
Adverse Events	X				X		X		X	
Review of Concomitant Medications	X				X		X		X	
CT Chest								X 		
CT Abdomen								X 		
Bone Marrow Aspirate and/or Biopsy								X 		X 
Research Tests		ı	1	ı			1	•		•
Bone Marrow Aspirate and/or Biopsy 								X 		X 
Peripheral Blood 	X				X		X	X 		X 

<sup>1A +/- 4 day window will be allowed for completion of scheduled clinic visits (i.e. holidays, travel delays, site closures, other reasons, etc.)

<sup>2A +/- 14 day window is allowed for this assessment.

<sup>3This evaluation may be perforned locally

<sup>4Survival assessment will be collected on an ongoing basis and at least every 3 months.

<sup>5If clinically indicated

<sup>2Head and neck examination can be performed as part of general physical exam, and consist of visual inspection of the oral mucosa and lymph node palpation.

<sup>3A window of +/- 21 days of scheduled visit is allowed for completion of these assessments.

<sup>4CT chest at Cycle 3, Day 28 will be performed if considered clinically indicated at the discretion of treating physicians (e.g. monitoring infection or pulmonary nodules).

<sup>5CT abdomen at Cycle 3, Day 28 will be performed if splenomegaly present on screening CT abdomen.

<sup>63-5ml of bone marrow aspirate will be collected in an EDTA-containing syringe.

<sup>73 green or purple top tubes (10cc tubes) will be collected for all patients at the specified time-points.

<sup>8This test may be done locally

The bone marrow aspirate and/or biopsy may be performed for assessment of response at the end of the third retreatment cycle OR during a subsequent re-treatment cycle when clinically indicated. The timing also applies for research samples.

10 ECGs are to be performed every 3 months after Cycle 3 of Re-Treatment

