**Table 1: Evaluation on Study** 

Phase	Screening	Study Visits											
Cycle		1		2		3	4 5			6			
Day 	-28 to -1	Day 1	Day 8	Day 15	Day 22	Day 1	Day 15	Day 1	Day 28+/-4	Day 1 	Day 1	Day 1	Day 28+/-4
Informed Consent	X												
History and Physical Exam	X	X				X		X		X	X	X	
Head and Neck Exam 	X	X				X					X		
ECG	X	X		X12		X		X		X			
Serum Pregnancy Test 	X												
Dermatology Exam 	X					X					X		
CBC w/ diff, Platelets	X	X	X12	X12	X12	X	X 	X	X	X	X	X	X
Smear Review	X	X	X12	X12	X12	X		X		X	X	X	
COMP, LDH	X	X				X		X	X	X	X	X	X
Phosphorus, Uric Acid	X	X	X 	X 	X 								
PT/PTT	X												
HIV, Hepatitis B and C	X												
Adverse Events		X				X		X		X	X	X	
Review of Concomitant Medications	X	X				X		X		X	X	X	
CT Chest	X								X 				
CT Abdomen	$X^6$								X 				
Bone Marrow Aspirate and/or Biopsy	X								X				$X^8$
Research Tests													
Bone Marrow Aspirate and/or Biopsy	X 					X 			X 				X 
Peripheral Blood 	X	X 	X 	X 	X 	X		X	X	10.0			X8

<sup>1A +/- 4 day window will be allowed for completion of scheduled clinic visits (i.e. holidays, travel delays, site closures, other reasons, etc.) A +/- 7day window is allowed for Cycle 4 Day 1 to allow the adequate time for bone marrow response evaluation from Cycle 3 Day 28.

<sup>2Head and neck examination can be performed as part of general physical exam, and consist of visual inspection of the oral mucosa and lymph node palpation.21

<sup>3In women of child-bearing potential, serum pregnancy test should be obtained within 7 days prior to start of treatment.

<sup>4A window of +/- 21 days of scheduled visit (with exception of screening) is allowed for completion of these assessments.

<sup>5CT chest at Cycle 3, Day 28 will be performed if considered clinically indicated at the discretion of treating physicians (e.g. monitoring infection or pulmonary nodules).

<sup>6CT abdomen at screening will be performed if patient has intact spleen.

<sup>7CT abdomen at Cycle 3, Day 28 will be performed if splenomegaly present on screening CT abdomen.

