# g. AEs of Special Interest (AESIs)

AESIs are a subset of Events to Monitor (EtMs) of scientific and medical concern specific to the product, for which ongoing monitoring and rapid communication by the Investigator to the Sponsor is required. Such an event might require further investigation in order to characterize and understand it. Depending on the nature of the event, rapid communication by the trial Sponsor to other parties (e.g., Regulatory Authorities) may also be warranted.

Adverse events of special interest for this study include the following:

- Cases of potential drug-induced liver injury that include an elevated ALT or AST in combination with either an elevated bilirubin or clinical jaundice, as defined by Hy's law: Treatment-emergent ALT or AST > 3 × ULN in combination with total bilirubin > 2 × LILN
  - Treatment-emergent ALT or AST > 3 × ULN in combination with clinical jaundice
- Data related to a suspected transmission of an infectious agent by the study drug (STIAMP), as defined below:
  - Any organism, virus, or infectious particle (e.g., prion protein transmitting transmissible spongiform encephalopathy), pathogenic or non-pathogenic, is considered an infectious agent. A transmission of an infectious agent may be suspected from clinical symptoms or laboratory findings that indicate an infection in a patient exposed to a medicinal product. This term applies only when a contamination of the study drug is suspected
- Acute Kidney Injury
- Bone Marrow Toxicity
- Cutaneous Squamous Cell Carcinomas
- Gastrointestinal Polyps
- Hypersensitivity and Severe Cutaneous Reactions
- Liver Injury
- New/Second Primary Melanomas
- Non cutaneous Squamous Cell Carcinomas
- Pancreatitis
- Photosensitivity
- Potentiation of Radiation Toxicity
- Progression of RAS Mutant Malignancies
- QT Prolongation
- Retinal Vein Occlusion
- Uveitis
- VII Nerve Paralysis

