# 11.8 Cutaneous Squamous Cell Carcinoma

Cutaneous squamous cell carcinoma (cuSCC) is defined as an AE of special interest. Investigator and patient should perform routine skin examination at least once per cycle (28 days). Suspicious lesions or rashes should be referred to a dermatologist. A dermatologist should perform a full skin exam during screening/baseline, after 4 weeks of treatment, and every 12 weeks thereafter until discontinuation of the drug. Patients who withdrew from the study for any reason will be followed for SCC evaluation for 6 months after study drug discontinuation, start of new antineoplastic therapy, or until death, withdrawal of consent, or lost to follow up, whichever occurs first. Additionally, at baseline, the dermatologist will perform a complete dermatological history of prior medications, non-melanoma skin cancers, including SCC and actinic keratosis and their associated treatments, and risk factors for development of cutaneous malignancies (e.g. radiation therapy, sun exposure, phototherapy, use of tanning beds, genetic conditions, and immunosuppression).

Any lesion at baseline or during treatment that is clinically suspected of representing a cuSCC, basal cell carcinoma, actinic keratosis, primary melanoma, or other skin condition identified by the dermatologist should be completely resected by a dermatologist and submitted for pathologic review. A dose reduction is not indicated for this adverse event.

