# 11.9 Non-Cutaneous Squamous Cell Carcinoma

- Head and neck examination: A thorough head and neck examination to monitor for noncutaneous SCC, consisting of at least visual inspection of the oral mucosa and lymph node palpation, will be performed by the treating physician during screening/baseline, after 4 weeks of treatment, and every 12 weeks thereafter until a maximum of 6 months after discontinuation of study drug or at the start of new antineoplastic therapy, death, withdrawal of consent, or lost to follow up whichever occurs first.
- Chest CT scans: A chest CT scan will be performed during screening/baseline (up to 28 days prior to start of treatment) and, if considered clinically indicated at the discretion of treating physicians, at Cycle 3 Day 28.

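### Table 3 fixes no dermatology or head and neck exam after Cycle 3 Day 1 of open-ended re-treatment, although Sections 11.8 and 11.9 set both every 12 weeks on drug

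*Combined protocol and SAP*

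**What the plan says.** Section 11.8 sets a dermatologist's full skin exam at baseline and then "after 4 weeks of treatment, and every 12 weeks thereafter until discontinuation of the drug". Section 11.9 sets the head and neck exam at baseline and then "after 4 weeks of treatment, and every 12 weeks thereafter until a maximum of 6 months after discontinuation of study drug". Neither section mentions re-treatment, either to include it or to exclude it. Both define the exams by time on drug.

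For the first course, the schedule headed "Table 1: Evaluation on Study" marks both exams at Cycle 2 Day 1 and Cycle 5 Day 1.

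Re-treatment is covered by Sections 4.2 and 9.1. It lasts until progression or for as long as the physician chooses, with no maximum number of cycles, and its assessments are those of the table headed "Table 3: Re-Treatment Evaluation on Study". In that table:

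- The head and neck row is marked at Cycle 1 Day 1 and Cycle 2 Day 1 only.
- The dermatology row is marked at Cycle 3 Day 1 and in the as-indicated column.
- The recurring Cycle X Day 1 column is blank for both.
- Footnote 2 adds: "Head and neck examination can be performed as part of general physical exam". A physical exam is marked on each Cycle X Day 1.

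**The concern.** The rule in Section 11 depends on exposure, and re-treatment is exposure to the same drug for a period that may exceed the six-cycle first course. Yet the schedule for that period carries fewer fixed exams than the first course, and none after Cycle 3 Day 1.

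The exams look for cutaneous and non-cutaneous squamous cell carcinoma. Both are adverse events of special interest: Section 11.2.4 g lists "Non cutaneous Squamous Cell Carcinomas" alongside the cutaneous form. Safety and tolerability is the first secondary objective in Section 2.0. If sites work from Table 3, surveillance for these events becomes lighter in the longest exposures, and findings from re-treatment are not collected on the same basis as those from the first course.

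**Working it through.** The plan gives no figure to reproduce. The check sets the marks side by side and turns the 12-week rule into study days.

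**Marks read by column**

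| Schedule | Head and neck | Dermatology |
|---|---|---|
| Table 1 (first course) | Screening, C1D1, C2D1, C5D1 | Screening, C2D1, C5D1 |
| Table 3 (re-treatment) | C1D1, C2D1 | C3D1, then as indicated |

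Over six cycles, counting after Day 1, Table 1 fixes 2 exams of each type and Table 3 fixes 1 of each. A table-reading fault is unlikely, because the physical exam, ECG and blood count rows of Table 3 line up with the same column headings.

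**Days on which exams fall due.** Cycles are 28 days (Section 4.2), so Day 1 of cycle c is study day 28 × (c − 1) + 1.

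- C2D1 = 28 × 1 + 1 = Day 29 (week 4)
- C3D1 = 28 × 2 + 1 = Day 57 (week 8)
- C5D1 = 28 × 4 + 1 = Day 113 (112 days, or 16 weeks, on drug)

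The 12-weekly exams fall at 29 + 84k: Days 113, 197, 281, 365, 449, 533, 617. Table 1's marks at C2D1 and C5D1 match weeks 4 and 16 exactly.

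**Unmarked 12-weekly exams of each type.** The documents do not give the length of re-treatment, so three lengths are assumed.

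| Assumed length | Last day | Clock from Day 29 | Clock from Day 57 |
|---|---|---|---|
| 6 cycles | 168 | 1 | 1 |
| 12 cycles | 336 | 3 | 3 |
| 24 cycles | 672 | 7 | 7 |

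The last column applies to dermatology only. It runs the 12 weeks from the C3D1 exam: Days 141, 225, 309, 393, 477, 561, 645. In the long run the rate is 365.25 / 84 = 4.35 unmarked exams of each type per year on drug.

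**How the C3D1 skin exam is counted.** Table 3 footnote 3 says: "A window of +/- 21 days of scheduled visit is allowed for completion of these assessments". That places the exam on Days 36 to 78 (57 ± 21). The same window around the 4-week exam is Days 8 to 50 (29 ± 21). The two overlap on Days 36 to 50, so the counts above credit the C3D1 exam as the 4-week exam. This is lenient, because an exam done on Day 57 itself lies outside Days 8 to 50. The same window around Day 113 is Days 92 to 134, which the C3D1 exam cannot reach.

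**Comparison with the ECG.** Section 11.10 sets ECGs every 12 weeks in the long term. Table 3 carries that forward: Cycle X Day 1 is marked, and footnote 10 requires an ECG every 3 months after Cycle 3. The two cancer-surveillance exams have no such footnote.

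**The case against.** The strongest reply is that Section 11 is part of the protocol. If its rule depends on being on drug, the exams remain required in re-treatment and Table 3 removes nothing. That stands: this is a conflict between text and schedule, and it causes missed exams only where a site follows the table. But Section 9.1 names Table 3 as the plan for these patients, so that reading is a natural one.

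A second reply is that the lighter dermatology schedule was intended, since Table 3 has its own as-indicated column and the post-treatment table also appears to make the skin evaluation conditional. However, Section 11.8 was not changed to match, and the head and neck row has no as-indicated mark. Table 2 schedules a head and neck exam every 3 months after the last dose, so a patient off drug has a fixed recurring exam and a patient on long re-treatment has none.

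Third, other safeguards remain. Section 11.8 asks investigator and patient to check the skin every cycle and sends suspicious findings to a dermatologist. The head and neck exam is a brief inspection and palpation that fits the physical exam marked on each Cycle X Day 1, and adverse events are recorded at that visit. These narrow the gap. However, footnote 2 permits the head and neck exam without scheduling it, and the per-cycle skin check is separate from the dermatologist's exam.

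Finally, the two dermatology clocks do not agree at every length. At 5 cycles (Day 140) the counts are 1 and 0, and at 8 cycles (Day 224) they are 2 and 1. Counted from C3D1, the first unmarked skin exam is Day 141 (20 weeks) rather than Day 113. This is correct, but it shifts the dermatology count by at most one exam.

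**Conclusion.** The concern holds as a minor point. Table 3 does not carry the 12-weekly exams of Sections 11.8 and 11.9 into re-treatment, although Table 1 carries them through the first course. For head and neck, the first unmarked exam falls at Day 113, after 16 weeks on drug. For dermatology it falls at Day 113 or Day 141, depending on the clock. One further exam of each type is unmarked every 84 days after that.

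The counts of 1, 3 and 7 rest on the assumed lengths of 6, 12 and 24 cycles and on crediting the C3D1 skin exam as the 4-week exam. The conclusion also rests on reading Sections 11.8 and 11.9 as covering all time on drug, which their wording supports but does not spell out for re-treatment.

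The two-stage design and the primary endpoint are unaffected. Accrual closed on 17 August 2016 (Section 1.0). The version approved in June 2022 still allows re-treatment, but the documents do not say how many patients are in it or could enter it, so the practical benefit may be small.

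**What to change.** In Table 3:

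- Mark the dermatology exam at Cycle 2 Day 1. The Cycle 3 Day 1 mark can move there, so no exam is added.
- Mark both exams at Cycle 5 Day 1 and every 12 weeks thereafter while on drug, in line with Sections 11.8 and 11.9 and Table 1. A footnote like the one for the ECG would do.
- Keep the as-indicated dermatology entry as an addition to the fixed exams.

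The cost is an edit to two table rows. For each re-treated patient it means about one skin exam per 12 weeks, which footnote 8 allows to be done locally, and one head and neck inspection per 12 weeks within a physical exam that is already scheduled. Section 11 already asks for both on drug, so the change aligns the schedule with an existing rule.

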# 11.0 TOXICITIES/SIDE EFFECTS

# 11.1 Expected Side Effects of Vemurafenib

Although vemurafenib has been extensively studied in patients with melanoma in phase I, II and III trials, the side effects in patients with HCL are unknown. Based on clinical experience in patients with melanoma, following adverse events can be expected at the dose of 960mg b.i.d. Guidelines for management of the toxicity are given in Section 9.2.

- Common: rash, photosensitivity, pruritus, palmar-plantar erythrodysesthesia (PPE), cutaneous SCC, fatigue, arthralgia, dry skin, mild hair loss and acute kidney injury
- Uncommon: increased AST, ALT, alkaline phosphatase and bilirubin, fever, nausea, vomiting, diarrhea, anorexia, weight loss, headache, neuropathy, altered taste
- Rare: pancytopenia, pancreatitis, conjunctivitis, pericarditis, renal impairment, dysphagia, arthritis, gastrointestinal polyps, allergic reactions, Stevens-Johnson syndrome, drug reaction with eosinophilia and systemic symptoms (DRESS), retinal vein occlusion, Dupuytren's contracture and plantar fibromatosis, Peripheral Edema.

#### 11.2 Assessments of Adverse Events

# 11.2.1 Adverse Events

An adverse event (AE) is any unfavorable and unintended sign, symptom, or disease temporarily associated with the use of an investigational medicinal product or other protocol-imposed intervention, regardless of attribution.

This includes the following:

- AEs not previously observed in the subject that emerge during the protocol-specified AE reporting period, including signs or symptoms associated with HCL that were not present prior to the AE reporting period.
- Complications that occur as a result of protocol-mandated interventions
- If applicable, AEs that occur prior to assignment of study treatment associated with medication washout, no treatment run-in, or other protocol-mandated intervention.
- Preexisting medical conditions (other than the condition being studied) judged by the investigator to have worsened in severity or frequency or changed in character during the protocol-specified AE reporting period.

To ensure consistency of AE and SAE (see below in Section 11.2.2) causality assignments, the following general guidelines should be applied:

- Yes: There is a plausible temporal relationship between the onset of the AE and administration of vemurafenib and the AE cannot be readily explained by the subject's clinical state, intercurrent illness, or concomitant therapies; and/or the AE follows a known pattern of response to vemurafenib; and/or the AE abates or resolves upon discontinuation of vemurafenib or dose reduction and, if applicable, reappears upon re-challenge.
- No: Evidence exists that the AE has an etiology other than vemurafenib (e.g., preexisting
  medical condition, underlying disease, intercurrent illness, or concomitant medication); and/or
  the AE has no plausible temporal relationship to vemurafenib administration (e.g., cancer
  diagnosed 2 days after first dose of study drug).

Expected AEs are those adverse events that are listed or characterized in the Package Insert (P.I.) or current Investigator Brochure (I.B.). Unexpected AEs are those not listed in the P.I. or current I.B. or not identified. This includes AEs for which the specificity of severity is not consistent with the description in the P.I. or I.B. For example, under this definition, hepatic necrosis would be unexpected if the P.I. or I.B. only referred to elevated hepatic enzymes or hepatitis.

Toxicity will be graded and recorded using the NCI Common Toxicology Criteria version 4.0. Clinically significant adverse events will be noted and compared to the baseline condition. Adverse events that will be noted will include expected side effects, and any other clinically significant symptom or laboratory value. An assessment will be made concerning the severity of the event, and if the event appears to be related to the study drug. Adverse events, toxicity grading, and attributions will be recorded in the electronic database by the Clinical Research Associate (CRA) after review of the data by the Principal Investigator.

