#### 6.0 CRITERIA FOR SUBJECT ELIGIBILITY

# 6.1 Subject Inclusion Criteria

- 1. ≥ 18 years of age
- 2. Histologically confirmed classical HCL with one of the following:
  - Intolerance to purine analogs or considered to be poor candidates for purine analogbased therapy
  - Failure to achieve any response (CR or PR) to the initial purine analog-based therapy
  - Relapse ≤ 2 years of purine analog-based therapy
  - ≥ 2 relapses

Histologic confirmation of diagnosis will be performed at MSKCC or a participating site.

- 3. Patients who meet the standard treatment initiation criteria, as defined by ANC ≤1.0, Hgb ≤ 10.0 or PLT ≤100K
- 4. ECOG performance status of 0-2
- 5. Acceptable pre-study organ function during screening as defined as: Total bilirubin ≤ 1.5 times the upper limit of normal (ULN), aspartate aminotransferase (AST) and alanine aminotransferase (ALT) ≤ 2.5x ULN, and serum creatinine ≤ 1.5x ULN
- 6. Electrocardiogram (ECG) without evidence of clinically significant ventricular arrhythmias or ischemia as determined by the investigator and a rate-corrected QT interval (QTc, Bazett's formula) of < 480 msec.

- 7. For women of childbearing potential, agreement to the use of two acceptable methods of contraception, including one barrier method, during the study and for 6 months after discontinuation of vemurafenib
- 8. For men with female partners of childbearing potential, agreement to use a latex condom and to advise their female partner to use an additional method of contraception during the study and for 6 months after discontinuation of vemurafenib
- 9. Negative serum pregnancy test within 7 days of commencement of treatment in premenopausal women.
- 10. Agreement not to donate blood or blood products during the study and for at least 6 months after discontinuation of vemurafenib; for male partners, agreement not to donate sperm during the study and for at least 6 months after discontinuation of vemurafenib
- 11. Ability to understand and willingness to sign a written informed consent document. Willingness and ability to comply with scheduled visits, treatment plans, laboratory tests, and other study procedures.

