# c. Preexisting Medical Conditions

A preexisting medical condition is one that is present at the start of the study. Such conditions should be reported as medical and surgical history. A preexisting medical condition should be re-assessed throughout the trial and reported as an AE or SAE only if the frequency, severity, or character of the condition worsens during the study. When reporting such events, it is

important to convey the concept that the preexisting condition has changed by including applicable descriptors (e.g., "more frequent headaches").

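### Sections 11.2.1 and 11.2.4(c) do not agree on whether a cytopenia present at entry as part of HCL becomes an adverse event when it deepens on treatment

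*Combined protocol and SAP*

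**What the plan says.** Three pieces of current text bear on a blood count that is low at entry and then falls further.

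- **Section 11.2.1, definition and list.** The opening sentence is broad: an AE is "any unfavorable and unintended sign, symptom, or disease temporarily associated with the use of an investigational medicinal product", whatever its attribution. The list beneath it covers events not seen before, "including signs or symptoms associated with HCL that were not present prior to the AE reporting period". It then covers "Preexisting medical conditions (other than the condition being studied) judged by the investigator to have worsened in severity or frequency".
- **Section 11.2.1, closing paragraph.** Clinically significant events are compared with baseline. What is noted takes in expected side effects and "any other clinically significant symptom or laboratory value".
- **Section 11.2.4(c).** "A preexisting medical condition is one that is present at the start of the study". Such a condition is "reported as an AE or SAE only if the frequency, severity, or character of the condition worsens during the study". HCL is not excepted, and there is no cross-reference to Section 11.2.1.

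Eligibility makes this relevant to everyone enrolled. Inclusion criterion 3 in Section 6.1 admits "Patients who meet the standard treatment initiation criteria, as defined by ANC ≤1.0, Hgb ≤ 10.0 or PLT ≤100K". Among the AEs of special interest in Section 11.2.4(g) is "Bone Marrow Toxicity", with no definition relative to baseline. Section 11.1 lists pancytopenia as a rare expected effect and says that side effects in HCL are not known. Section 14 plans only to tabulate safety data over all subjects and gives no rule for counts already abnormal at entry.

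**The concern.** Safety and tolerability in HCL is secondary objective 1. In patients who enter cytopenic, whether the drug lowers counts further is among the safety questions most specific to this population. The list in Section 11.2.1 appears to leave that event out, while Section 11.2.4(c) appears to require it.

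Two things are at stake. In a multi-center trial, sites can follow different texts, so a tabulated rate of haematologic AEs would mix two definitions. Where the list is applied literally, the rate would also be too low in the blood lines that were already low. Because Section 14 makes no adjustment for baseline, nothing in the planned analysis would reveal or repair either problem.

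**Working it through.** The plan states no figure here, and the point depends on no error rate or sample-size formula. The check is to apply each text to the possible cases.

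**Step 1: who can be affected.** Criterion 3 joins its three thresholds with an or. Each patient therefore has at least one low line among ANC, haemoglobin and platelets, but not necessarily all three. Section 3.1 describes progressive pancytopenia as characteristic of HCL, so a low line at entry would ordinarily be read as a sign of the studied condition.

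**Step 2: apply the rules.**

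| Case on treatment | 11.2.1 list | 11.2.1 closing paragraph | 11.2.4(c) | Do they agree? |
|---|---|---|---|---|
| Line normal at entry, becomes low | AE (new) | Noted if clinically significant | Not applicable, since not present at entry | Yes |
| Line low at entry from a cause other than HCL, falls further | AE (worsened other condition) | Noted if clinically significant | Reported | Yes |
| Line low at entry as part of HCL, falls further | Neither item covers it: not new, and HCL is carved out | Noted if clinically significant | Reported | **No** |

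**Step 3: look for a tie-break.** No text ranks the three. The closing paragraph turns on clinical significance, which is left undefined, and does not say how to treat a line already abnormal at entry. If it is taken to capture the third case, Section 11.2.1 is in tension with its own list. If it is not, the conflict with Section 11.2.4(c) stands.

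**Step 4: is a filter by cause needed at recording?** Section 11.2.1 defines an AE regardless of attribution, and its causality guideline already gives underlying disease as a ground for answering no. Attributions go into the database. Falls driven by HCL can therefore be separated after they are recorded, and the carve-out is not needed for that purpose.

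**Step 5: grading.** The closing paragraph of Section 11.2.1 names version 4.0 of the NCI toxicity criteria, whereas Section 11.2.4(e) names version 5.0. Any statement of worsening by grade needs one version.

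**The case against.** The strongest reply is that Section 11.2.1 does not prohibit anything. Its list is introduced as illustrative, the parenthesis limits one item only, and both the opening definition and the closing paragraph are wide enough to take in a significant fall in counts. That is correct, and it means the section cannot be said to exclude these events outright. It does not settle the matter: the parenthesis has no function unless it leaves worsening HCL out, and a site applying it in good faith would omit the event.

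A second reply is that a fall caused by vemurafenib is not a worsening of HCL, so the carve-out merely separates progression from toxicity. That is a reasonable purpose, but the wording gives no way to tell the two apart when the event is recorded. The conflict does arise only when the fall is regarded as HCL.

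A third is that Section 11.2.4(c) states a necessary condition for reporting, not a sufficient one, and so could be read together with the list. This is possible, but its natural reading is an instruction to report worsening.

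A fourth is that other routes exist. Bone marrow toxicity is an AE of special interest, and a footnote in Section 11.2.4(e) sends Grade 4 and 5 events to SAE reporting. These may catch severe events. However, the footnote belongs to a scale for events that CTCAE does not list, and neither route says how to count a line that was already low.

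A reader might go further and infer that the trial would report 0 of 36 such events, with an exact two-sided 95% upper limit of 1 − 0.025^(1/36) = 9.7%, and so exclude a true rate of 10% or more. The documents do not support that. It needs every site to take the strictest reading and ignore the other texts, it needs an assumed rate of worsening, and Section 14 plans no such interval. Section 3.6 reports very little haematologic toxicity in melanoma, so the true rate may well be low.

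**Conclusion.** The inconsistency is real and sits in current text. It concerns one situation: a line low at entry, regarded as part of HCL, that falls further on treatment. Any of the 36 planned patients could meet it, but only those whose low line actually falls are affected. New cytopenias, and cytopenias from other causes, count under both rules.

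The likely consequences are uneven recording across sites and some undercounting of haematologic toxicity where the list is followed literally. The size is unknown, because the documents give neither the rate of on-treatment worsening nor the practice at sites. Saying that all 36 patients are affected, or that these events will go unrecorded, would claim more than the text allows.

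The effect is confined to the descriptive safety objective. The response endpoint, the two-stage rule and the sample size are untouched. The point merits correction because the remedy is cheap and the question is specific to this population.

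**What to change.** 1. **One reconciling sentence**, placed in Section 11.2.1 and referred to in Section 11.2.4(c), for example: *A worsening from baseline in ANC, haemoglobin or platelets during the AE reporting period is recorded as an AE whether or not that line was low at entry; presumed cause is entered in the attribution field.* Amend the parenthesis in the list and the closing paragraph of Section 11.2.1 to match.
2. **One table in Section 14**: for each of the three lines, baseline grade by worst on-treatment grade, from the blood counts already scheduled in Tables 1 and 3.
3. **One CTCAE version**, stated once and used for both.

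Accrual closed in August 2016, so for patients already treated the table does most of the work, because it does not depend on how sites recorded AEs. It does assume that the count values are held centrally; some interim counts may be done locally, so their availability should be confirmed. No new visits or tests are needed.

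The small downside is that some falls driven by disease will appear as AEs. The attribution field and the baseline-by-worst-grade layout help the reader to identify them. A line already in the highest grade at entry cannot rise further, and the table will show it as unchanged.
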